2.11 Analyses supporting secondary objectives – patient-reported outcomes

To assess the effect of JDQ443 on patient-reported lung cancer symptoms, health related quality of life, and health status, as well as the participants perception of overall side effects via patient-reported outcomes (PRO) questionnaires are secondary objectives of the study.

Data collected in the following patient-reported outcomes questionnaires up to the data cut-off date for the primary analysis will be analyzed by cohort (A and B): the NSCLC-SAQ and the EORTC QLQ-C30. The FAS will be used for analyzing PRO data. No multiplicity adjustment will be applied.

The NSCLC disease related symptoms as measured by the NSCLC-SAQ and physical function scale score of the QLQ-C30 are identified as the primary PRO variables of interest. Global health status (GHS) and role function scale scores of the QLQ-C30 is identified as secondary PRO variables of interest.

Scoring of PRO data and methods for handling of missing items or missing assessments will follow the scoring manual and user guide for each respective participant questionnaire ([Aaronson et al 1993](#), [Fayers et al 2001](#), [McCarrier et al 2016](#)). No imputation procedures will be applied for missing items or missing assessments.

2.11.2 Change from baseline

Change from baseline in the observed scores at each scheduled assessment timepoint using the time windows described in [Section 2.1.3.9](#) will be summarized for the following:

- NSCLC-SAQ total score, and each NSCLC-SAQ items/domains.
- EORTC QLQ-C30 all domains, subscales and items

Additionally, change from baseline at the time of each assessment will be plotted and summarized for the above variables.

Participants with an evaluable baseline score and at least one evaluable post-baseline score during the on-treatment period will be included in the change from baseline analyses.

2.11.3 Other analyses

Descriptive statistics will be used to summarize the observed scores of the EORTC QLQ-C30 and NSCLC-SAQ, at each scheduled assessment timepoint using the time windows described in [Section 2.1.3.9](#). All questionnaire data will be listed and those collected in the post-treatment period will be flagged in the listings.

The quality of completion of the PRO domain and total scores will be described for each scheduled assessment timepoint. In addition to the number and percentage of completed domain scores and the number and percentage of missing domain scores, the following categories of item-level missingness will be evaluated within each domain or measure:

- Number and percentage of participants who completed all questions
- Number and percentage of participants who completed the minimum requirement for scoring
- Number and percentage of participants who completed at least one question

The denominator for calculating percentages is the number of participants who remain in the study at each assessment.

Where available, the reasons for missing PRO data will be summarized. Additional analyses may be performed if deemed necessary. Such analyses will be defined in a separate PRO SAP.

[REDACTED]

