7.1.3 Overall Survival

All participants will enter the survival follow-up period once they complete the safety follow-up and efficacy follow-up after treatment discontinuation (whichever is longer). Survival status will be collected every 12 weeks (+/- 14 days) regardless of treatment discontinuation reason (except if consent is withdrawn or participant is lost to follow-up) until death, lost to follow-up, or withdrawal of consent for survival follow-up.

[figure not shown]
Additional survival assessments may be performed outside the 12-week follow-up schedules if a survival update is required due to safety or regulatory needs.

Survival information can be obtained via phone, and information will be documented in the source documents and relevant eCRFs. Information on the therapies received for NSCLC, if

any, after study treatment has been completed will be collected. All SAEs reported during this time period must be reported as described in Section 8.7.

Figure 7-1 illustrates study flow.

Figure 7-1 **Study Flow**

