7.2 Participant discontinuation from the study

Discontinuation from study is when the participant permanently stops receiving the study treatment and further protocol-required assessments or follow-up for any reason.

If the participant agrees, a final evaluation at the time of the participant's study discontinuation should be made as detailed in the assessment table (refer to Section 1.3).

See Section 6.6 for information on continued access to study treatment after the end of the study

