The following back-up options are available during the treatment period, efficacy follow-up (if applicable) and survival period for participants who might not return to the clinic: PRO completion can be done from home using a web-based application or by interview over the phone provided the interviewer has received the appropriate training on recording the participant's responses. These are only to be used if there is a valid reason for employing them

such as public health emergency, or patient unable to complete on provisioned device/web-based application (for more details, refer to vendor manual).

The NSCLC-SAQ, EORTC QLQ-C30, FACT GP5, PRO-CTCAE, PGIS-NSCLC and EQ-5D-5L PROs will be administered as indicated in Table 1-3 while the participant is on treatment, at EOT visit, during the post-treatment efficacy follow-up period (at corresponding imaging efficacy follow-up visits, if the participant is still followed for efficacy) and during the survival period.

- For participants who have discontinued study treatment due to progressive disease by RECIST 1.1 as assessed by BIRC and enter the safety and survival follow-up periods, NSCLC-SAQ, EORTC QLQ-C30, FACT GP5, PRO CTCAE, PGIS-NSCLC and EQ-5D-5L will be collected at EOT and every 12 weeks post progressive disease for a minimum of 3 timepoints.
- For participants, who continue study treatment beyond progressive disease by RECIST 1.1
 as assessed by BIRC, PROs will continue to be collected at the same timepoints as defined
 during the treatment period. Once the participants discontinue study treatment and enter
 safety and survival follow-up periods, NSCLC-SAQ, EORTC QLQ-C30, FACT GP5,
 PRO CTCAE, PGIS-NSCLC and EQ-5D-5L will be collected at EOT and every 12 weeks
 post progressive disease for a minimum of 3 timepoints.
- For participants who have discontinued study treatment for any other reason than progressive disease by RECIST 1.1 as assessed by BIRC and enter the efficacy follow-up period, PROs will be collected at EOT and every 12 weeks for NSCLC-SAQ, EORTC QLQ-C30, FACT GP5, PRO CTCAE, PGIS-NSCLC and EQ-5D-5L and at the time of progressive disease by RECIST 1.1 as assessed by BIRC. Following progressive disease by RECIST 1.1as assessed by BIRC, NSCLC-SAQ, EORTC QLQ-C30, FACT GP5, PRO CTCAE, PGIS-NSCLC and EQ-5D-5L will be collected every 12 weeks post progressive disease for a minimum of 3 timepoints.

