10.2.2 Definitions

Additional treatment	Medicinal products that may be used during the clinical trial as described in the protocol, but not as an investigational medicinal product (e.g. any background therapy)
Assessment	A procedure used to generate data required by the study
Biologic Samples	A biological specimen including, for example, blood (plasma, serum), saliva, tissue, urine, stool, etc. taken from a study participant
Clinical Outcome Assessment (COA)	A measure that describes or reflects how a participant feels, functions, or survives
Clinical Trial Team	A group of people responsible for the planning, execution and reporting of all clinical trial activities. Examples of team members include the Study Lead, Medical Monitor, Trial Statistician etc.
Coded Data	Personal Data which has been de-identified by the investigative center team by replacing personal identifiers with a code.
Cohort	A group of individuals who share a common exposure, experience or characteristic, or a group of individuals followed-up or traced over time
Cycles	Number and timing or recommended repetitions of therapy are usually expressed as number of days (e.g., q28 days)
Discontinuation from study	Point/time when the participant permanently stops receiving the study treatment and further protocol required assessments or follow-up, for any reason. No specific request is made to stop the use of their samples or data.
Discontinuation from study treatment	Point/time when the participant permanently stops receiving the study treatment for any reason (prior to the planned completion of study drug administration, if any). Participant agrees to the other protocol required assessments including follow-up. No specific request is made to stop the use of their samples or data.
Dosage	Dose of the study treatment given to the participant in a time unit (e.g. 100 mg once a day, 75 mg twice a day)
Electronic Data Capture (EDC)	Electronic data capture (EDC) is the electronic acquisition of clinical study data using data collection systems, such as Web-based applications, interactive voice response systems and clinical laboratory interfaces. EDC includes the use of Electronic Case Report Forms (eCRFs) which are used to capture data transcribed from source data/documents used at the point of care
End of the clinical trial	The end of the clinical trial is defined as the last visit of the last participant

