Efficacy follow-up 2	24 weeks after 24 weeks after EOT disposition date + 7 days	From 18 weeks after EOT disposition date + 8 days to 30 weeks after EOT disposition date + 7 days
Efficacy follow-up k ($k = 3, 4, \dots$) ^{\$}	$12 + (k-1) \times 12$ weeks after EOT disposition date + 7 days	From $(k-1) \times 12 + 6$ weeks after EOT disposition date + 8 days to $(k-1) \times 12 + 18$ weeks after EOT disposition date + 7 days

Time window	Planned visit timing	Time window definition
Post disease progression		
Survival follow-up 1	12 weeks after disease progression date	From PD date [#] to 18 weeks after PD date [#]
Survival follow-up 2	24 weeks after disease progression date	From 18 weeks after PD date [#] + 1 day to 30 weeks after PD date [#]
Survival follow-up 3	36 weeks after disease progression date	From 30 weeks after PD date [#] + 1 day to 42 weeks after PD date [#]
Survival follow-up k if available (k = 4, 5, ...)	12×k weeks after disease progression date	From 12×k-6 weeks after PD date [#] + 1 day to 12×k + 6 weeks after PD date [#]

* Study day 1 = date of first treatment, C1D1

Post treatment study day 1 = end of treatment date + 1 day

\$ The assessment “at disease progression” in efficacy follow-up should be the last visit in this period

It is the EOT visit date + 8 days for participants without efficacy follow-up

Table 2-3 Time windows for PROs: EORTC QLQ-C30

[figure not shown]
Time window	Planned visit timing	Time window definition
Baseline	On or before Study Day 1*	≤ Study Day 1*
On treatment		
Cycle 2 Day 1	Study Day 22	Study Days 2 – 32
Cycle 3 Day 1	Study Day 43	Study Days 33 – 53
Cycle k Day 1 (k≥ 4)	Study day d=(k-1)×21+1	Study days d-10 to d+10 For last cycle of dosing: from (k-1)×21-9 to EOT disposition date + 7 days Note: EOT visit data are included if obtained within 7 days of permanent discontinuation of study treatment.
Post treatment		
Efficacy follow-up, every 12 weeks		
Efficacy follow-up 1	12 weeks after EOT disposition date + 7 days	From EOT disposition date + 8 days to 18 weeks after EOT disposition date + 7 days
Efficacy follow-up 2	24 weeks after EOT disposition date + 7 days	From 18 weeks after EOT disposition date + 8 days to 30 weeks after EOT disposition date + 7 days
Efficacy follow-up k (with k = 3, 4, ...)	12+(k-1)×12 weeks after EOT disposition date + 7 days	From (k-1)×12+6 weeks after EOT disposition date + 8 days to (k-1)×12+18 weeks after EOT disposition date + 7 days

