4.6.2 EORTC QLQ-C30

The EORTC QLQ-C30 questionnaire contains 30 items and is composed of both multi-item scales and single-item measures. These include

- Five functional scales (physical, role, emotional, cognitive and social functioning),

- Three symptom scales (fatigue, nausea/vomiting, and pain),
- A global health status / QoL scale, and
- Six single items (dyspnea, insomnia, appetite loss, constipation, diarrhea and financial impact).

All scales and single-item measures range in score from 0 to 100. A high scale score represents a higher response level. Thus a high score for a functional scale represents a high/healthy level of functioning; a high score for the global health status represents a high quality of life, but a high score for a symptom scale represents a high level of symptomatology/problems. Note: This difference needs to be considered in the review and interpretation of the outputs.

QLQ-C30 scale scores will be generated by first obtaining the raw scores by averaging the item responses on the questions which contribute to the scale. Then a linear transformation will be used to standardize the raw score so that scores range from 0 to 100. This transformation is specified in the scoring manual provided by the developers. Scores in each scale will be generated if at least half of the items comprising the scale have been answered. For single item scales with missing responses and scales where less than half of the items have not been answered, scale scores will be set to missing.

5 References

Brookmeyer R and Crowley J (1982) A Confidence Interval for the Median Survival Time. Biometrics; 38:29-41.

Clopper C, Pearson ES (1934) The use of confidence or fiducial limits illustrated in the case of the binomial. *Biometrika*; 26(4):404-13.

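### PRO completion is divided by everyone still in the study, which understates it at treatment-cycle visits; separately, the SAP's QLQ-C30 missing-item sentence contradicts the sentence before it

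*SAP*

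**What the plan says.** **Denominator.** SAP 2.11.3 describes completion of the PRO domain and total scores at every scheduled timepoint. It counts participants who answered all questions, who answered enough for scoring, and who answered at least one. It then states: "The denominator for calculating percentages is the number of participants who remain in the study at each assessment". The windows in SAP 2.1.3.9 cover treatment-cycle visits as well as efficacy follow-up and post-progression visits. Protocol 9.4.4 asks for numbers completed and numbers missing, and names no denominator.

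**Who remains in the study.** Protocol 7.2: "Discontinuation from study is when the participant permanently stops receiving the study treatment and further protocol-required assessments or follow-up for any reason". The definitions in protocol 10.2.2 agree, and say of someone who stops treatment only: "Participant agrees to the other protocol required assessments including follow-up". Protocol 7.1.3 adds: "Survival status will be collected every 12 weeks (+/- 14 days) regardless of treatment discontinuation reason".

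**Which forms are owed after treatment.** Under protocol 8.6.1, participants who stop because of progression have questionnaires that "will be collected at EOT and every 12 weeks post progressive disease for a minimum of 3 timepoints". Those who stop for another reason owe forms at EOT, every 12 weeks in efficacy follow-up, at progression, and then on the same post-progression schedule. Those treated beyond progression stay on the treatment-period schedule.

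**QLQ-C30 scoring.** SAP 4.6.2 says a scale is scored once half or more of its items have been answered. The next sentence lists the cases in which the score is instead treated as missing, and it begins: "For single item scales with missing responses and scales where less than half of the items have not been answered, scale scores will be".

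**The concern.** A completion rate tells the reader how far to trust the PRO results. It should answer one question: of the participants due a form, how many returned it? A denominator that includes people with no form due mixes compliance with treatment discontinuation. The rate then falls as participants come off treatment, even if everyone who is asked complies, and a reader could take that fall for missing data.

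The scoring sentence is a separate matter. Its condition runs the wrong way, and it applies to every QLQ-C30 scale, including physical functioning, which is one of the two time-to-definitive-deterioration endpoints. The two points touch in one place: SAP 2.11.3 tabulates participants meeting the minimum requirement for scoring, and for the QLQ-C30 that requirement is set out in SAP 4.6.2.

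**Working it through.** The documents state no completion rate, so there is no figure of the plan's own to reproduce.

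**1. Denominator**

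At a treatment-cycle window, let S be the participants in the study, D those due the form, and C those who complete it.

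- Rate under SAP 2.11.3: C / S
- Rate among those due: C / D
- f = (S − D) / S, so C / S = (C / D) × (1 − f)

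The reported rate is lower than the rate among those due whenever any off-treatment participant is still followed.

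Illustration. S = 90 is the planned size of cohort A. The values of f and the completion rate of about 90% are assumptions. Counts are rounded to whole participants.

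| f | Not due | Due (D) | Completed (C) | Reported, C/90 | Among those due, C/D |
|---|---|---|---|---|---|
| 10% | 9 | 81 | 73 | 81.1% | 90.1% |
| 30% | 27 | 63 | 57 | 63.3% | 90.5% |
| 50% | 45 | 45 | 40 | 44.4% | 88.9% |

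With about 80% completion among those due, the reported rates are 65/90 = 72.2%, 50/90 = 55.6% and 36/90 = 40.0%. For cohort B (S = 30) with f = 30% and about 90% completion, 19/30 = 63.3% is reported against 19/21 = 90.5%.

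**2. QLQ-C30 sentence**

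Let a multi-item scale have m items, of which a are answered.

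- First sentence: score if a ≥ m/2.
- Second sentence, read literally: set to missing if m − a < m/2, that is, if a > m/2.

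| Items answered | First sentence | Second sentence, literal | Result |
|---|---|---|---|
| More than half | Score | Missing | Contradiction |
| Exactly half (m even) | Score | Not set to missing | No conflict |
| Fewer than half | No score | Not set to missing | Second sentence silent where it should apply |

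The documents do not give the number of items per scale, so this was checked for m = 1 to 5 as an assumed range; the inequalities do not depend on m. If the condition becomes a < m/2, the second sentence is the exact complement of the first in every case checked.

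**The case against.** **On the denominator.** The windows in SAP 2.1.3.9 are relative to each participant. The last cycle window closes 7 days after the EOT disposition date, and follow-up windows start from there. On that view, remaining in the study at an assessment could mean those to whom the assessment applies. A sensible programmer might do this, but the sentence does not say it. The windows assign data to visits; they do not decide who is counted, and being in the study is a defined status in the protocol.

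Part of the objection does stand. Off-treatment participants do owe forms at follow-up windows, so counting them there is right while a form is due. The plan also summarises available reasons for missing PRO data, and SAP 2.3.8 tabulates participants on treatment and in follow-up. These give context but do not correct the percentage.

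**On the scoring sentence.** The correct rule stands immediately before it. SAP 2.11 and protocol 8.6.1 and 9.4.4 all send scoring to the manual. Taken literally, the sentence would discard fully completed scales, so it is plainly a slip. That is accepted. But SAP 4.6 presents its text as rules needed for programming, so the contradiction should not be left there.

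**On size.** A reader might derive f from the updated sotorasib medians in protocol 2.2.3 (PFS 6.3 months, OS 12.5 months) and treat the result as an estimate for this trial. The documents do not support that. Those data come from another drug in pretreated patients, whereas this trial is first-line. The derivation would also assume exponential curves and treatment ending at progression, although treatment beyond progression is allowed.

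**Conclusion.** Both points hold, within limits.

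The denominator as written includes off-treatment participants who are not due cycle-visit forms, and it understates completion at those windows by the factor (1 − f). The direction follows from the definitions. The size does not: f is unknown, and the range of about 81% down to 44% rests on assumed f of 10% to 50% with about 90% completion among those due.

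The effect is confined to descriptive completion tables. A reader might infer that the deterioration or change-from-baseline results are themselves biased. They are not affected by this denominator, because they use on-treatment assessments and evaluable scores and the completion percentage does not enter them. No formal PRO tests are planned.

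The QLQ-C30 sentence is an internal contradiction. A reader might infer that validly scored scales will be blanked. That would happen only if the sentence were programmed literally against the one before it and against the manual. Even then it would not reach every scale the first sentence scores, since one with exactly half of an even number of items answered would keep its score. If it were programmed literally, scales with more than half of their items answered would be lost, and that would reach the QLQ-C30 change-from-baseline summaries and time to definitive deterioration in physical functioning.

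**What to change.** **SAP 2.11.3.** Replace the denominator with the participants expected to complete the form in that window:

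- treatment windows: participants on treatment, including those treated beyond progression;
- post-treatment windows: participants in the relevant follow-up with a form due. Because the post-progression forms are set only as a minimum of three, state when a form counts as due after the third.

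A second rate over the FAS may be shown beside it, labelled as such, so that attrition and compliance can be read separately.

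**SAP 4.6.2.** Delete the word *not* from the half-of-items condition, so that a scale is set to missing when fewer than half of its items have been answered.

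The cost is two reworded SAP sentences and the matching table specification. No new data are needed: treatment status, progression date and follow-up status are already collected.

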2.15 Interim analysis

The planned interim analyses for futility will be performed separately for each of the two cohorts. A separate interim analysis plan will provide details and specifications for the analyses.

2.15.1 Primary endpoint: ORR in cohort A

One IA is planned for cohort A based on approximately the first 30 evaluable participants. Evaluable participants are defined as enrolled participants who have been followed for at least two tumor assessments or have discontinued the study treatment earlier. The primary intent of the interim analysis is to stop the cohort early for lack of efficacy (futility).

The decision whether to continue or stop enrollment and/or treatment will be based on the predictive probability of success (PPoS). PPoS is the predictive probability of a positive conclusion of the study (regarding cohort A) if it continued beyond the interim analysis (i.e., until the final analysis), given the interim observed data (x) and successes among n participants.

$$\text{PPoS} = \text{Prob}[\text{Final observed ORR} \geq \text{[REDACTED]} x, n]$$

A minimally informative Beta distribution prior ([Neuenschwander et al 2008](#)) with prior mean equal to [REDACTED] will be used, i.e., the prior distribution will be Beta [REDACTED] for the PPoS calculation the interim analysis.

The cohort will be stopped for futility at the interim analysis if the observed ORR is \leq [REDACTED] corresponding to 9 or less responders (at least [REDACTED] responders out of 30 participants are required for the study to proceed). If the futility criterion is met, the predictive probability of observing a success in the future based on the existing data will be [REDACTED]

All evaluable participants in cohort A at the time of the data cut-off for the interim analysis will be used.

If futility is concluded, the enrollment of participants in the cohort will be stopped. The enrollment in cohort B will continue, if applicable.

[Table 2-9](#) provides the PPoS at the primary analysis based on different numbers of responders observed at the interim analysis. For [REDACTED] responders, PPoS exceeds [REDACTED] and the cohort will continue after the interim analysis.

Table 2-10 PPoS at the primary analysis based on various numbers of responders observed at the IA

Responders at IA out of 30 evaluable participants	Predictive probability of success (%)
5	[REDACTED]
6	[REDACTED]
7	[REDACTED]
8	[REDACTED]
9	[REDACTED]
10	[REDACTED]

Responders at IA out of 30 evaluable participants	Predictive probability of success (%)
11	[REDACTED]
12	[REDACTED]

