One interim analysis for futility to assess ORR by BIRC independently in each cohort is planned, when approximately the first 30 (cohort A) and approximately the first 15 participants (cohort B) have been enrolled and followed for at least 2 tumor assessments or have discontinued the study treatment earlier. The primary intent of the interim analyses is to allow an early assessment of the antitumor activity of JDQ443 and to discontinue the respective cohort early if lack of efficacy (futility) is observed. In case the IA of the two cohorts occurs at a similar time, the IAs will be reported together.

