5. Summary measure: ORR defined as the proportion of participants with a confirmed CR/PR as BOR, with its corresponding two-sided exact binomial 95% confidence interval and a summary of the reasons for 'NE' BOR.

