2.6 Analysis supporting primary objective(s)

The primary objective of the study is to assess the antitumor activity of JDQ443 single-agent as first-line treatment for participants with locally advanced or metastatic NSCLC whose tumors harbor a KRAS G12C mutation and a PD-L1 expression < 1%, regardless of STK11 mutation status (cohort A). The primary analysis of the primary and key secondary endpoint will be conducted when participants in the respective cohort who are still receiving study treatment will have completed at least 4 tumor assessments or discontinued earlier (approximately 24 weeks), provided that cohort A was not declared futile at the interim analysis.

Depending on the enrollment and follow-up of the participants in the two cohorts, the analysis of the primary and key secondary endpoint can also be analyzed at the same time.

The analysis will be based on the FAS and will include all participant data observed up to the cut-off date.

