2.6.1 Primary endpoint(s)

The primary clinical question of interest and the primary estimand are defined in [Section 1.2.1](#).

The primary endpoint is ORR, defined as the proportion of participants with a confirmed CR/PR as BOR. BOR is defined as the best response recorded from the start of the treatment until disease progression per RECIST 1.1 by BIRC. Complete and partial responses must be

confirmed by repeat assessments that should be performed not less than 4 weeks after the criteria for response were first met. Responses documented after the use of any new anti-neoplastic therapy will be considered as non-response (with the exception of protocol-allowed radiotherapy).

The BOR will be determined from response assessments undertaken while on treatment. In addition, only tumor assessments performed before the start of any further anti-neoplastic therapy (with the exception of protocol-allowed radiotherapy) will be considered in the assessment of BOR.

BOR for each participant is determined from the sequence of overall (lesion) responses according to the following rules:

- CR = at least two determinations of CR at least 4 weeks apart before progression;
- PR = at least two determinations of PR or better at least 4 weeks apart before progression (and not qualifying for a CR);
- SD = at least one SD assessment (or better) > 5 weeks after start of treatment (and not qualifying for CR or PR);
- Non-CR/non-PD* = at least one Non-CR/non-PD assessment > 5 weeks after start of treatment (and not qualifying for CR);
- PD = progression ≤ 13 weeks after start of treatment (and not qualifying for CR, PR or SD);
- NE = all other cases (i.e., not qualifying for confirmed CR or PR and without SD after more than 5 weeks or early progression within the first 13 weeks).

* For participants with only non-measurable disease present at baseline. A non-CR/non-PD response is considered equivalent to an SD response for the ORR determination and participants will be considered “non-responders”.

Participants with ‘NE’ BOR will be summarized by reason for having NE status. The following reasons will be used:

- No valid post-baseline assessment
- All post-baseline assessments have overall lesion response NE
- New anti-neoplastic therapy started before first post-baseline assessment
- SD too early (≤ 5 weeks after start of treatment)
- PD too late (> 13 weeks after start of treatment)

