2.6.3 Handling of intercurrent events

The primary analysis will account for different intercurrent events as follows:

1. Discontinuation of study treatment: Tumor assessment data collected after discontinuation of study treatment for any reason will be included to derive BOR (treatment policy strategy).
2. Start of a new anti-neoplastic therapy: If any new anti-neoplastic therapy is initiated, responses documented after the use of new anti-neoplastic therapy will be considered as non-response (composite strategy). Protocol-allowed radiotherapy is exempted.
3. Any public health emergency as declared by local or regional authorities, i.e., pandemic, epidemic or natural disaster: Tumor assessment data collected irrespective of such unforeseen events will be considered for the BOR (treatment policy strategy).

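### Unless the separate interim plan deals with it, the cohort A futility rule scores a response first seen at scan 2 as a non-response in participants with only two scans, a small avoidable bias towards stopping.

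*SAP*

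**What the plan says.** **Endpoint at the interim.** SAP 1.1: "One interim analysis for futility to assess ORR by BIRC independently in each cohort is planned". Neither document gives a separate interim definition of response. SAP 1.2.1 has "ORR defined as the proportion of participants with a confirmed CR/PR as BOR", and SAP 2.6.1 requires CR and PR to be "confirmed by repeat assessments that should be performed not less than 4 weeks after the criteria for response were first met". Under the BOR rules in SAP 2.6.1, a single unconfirmed CR or PR more than 5 weeks after treatment start is SD.

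**Who is counted.** SAP 1.1 times the interim at about 30 (cohort A) and 15 (cohort B) participants who "have been enrolled and followed for at least 2 tumor assessments or have discontinued the study treatment earlier". SAP 2.15.1 defines evaluable participants on the same two-scan criterion, as "enrolled participants who have been followed for at least two tumor assessments or have discontinued the study treatment earlier". Protocol 4.1, 4.6, 9.8.1 and 9.8.2 and SAP 2.15.2 also use two assessments. SAP 4.5 puts scans at weeks 6, 12, 18 and 24.

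**Boundary.** Cohort A stops at 9 or fewer responders of 30. The cohort A prior, the PPoS threshold, the PPoS table and most of the operating characteristics are redacted, as is the cohort B boundary.

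**Primary analysis.** This takes place when participants "who are still receiving study treatment will have completed at least 4 tumor assessments or discontinued earlier" (SAP 2.6).

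**Deferral.** SAP 1, 2.1 and 2.15 leave the interim specifications to a separate plan, which was not available for review.

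**The concern.** Two scans are enough to enter the denominator. They are enough to enter the numerator only if the response was already present at scan 1. A response first seen at week 12 cannot ordinarily be confirmed until the week 18 scan. Until then the participant is SD, hence a non-responder, although the same response can count at the primary analysis. PPoS as described conditions only on the interim count and sample size, with no term for responses awaiting confirmation.

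An immature count is therefore compared with a fixed boundary, and the error runs one way, towards stopping a cohort that works. The first-in-human data in protocol 2.2.3.3.1 show that pending responses do occur with this drug: 7 of 20 NSCLC patients had a confirmed PR and 2 more had one not yet confirmed. That sample is small, pretreated and investigator-assessed. It illustrates the mechanism and does not estimate its size.

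**Working it through.** **1. Inputs from the documents.** Interim n = 30, stop at 9 or fewer (SAP 2.15.1). Final N = 90 (SAP 3). Success needs an exact 95% lower bound of at least 35% (SAP 2.6.2). True ORR 50% is the one readable alternative (protocol 9.9.1).

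**2. Final rule.** The Clopper-Pearson lower bound is 0.3396 for 40/90 and 0.3502 for 41/90, so success needs at least 41 responders. Any redacted observed-ORR criterion is not included.

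**3. The plan's own boundary.** PPoS = P(x + BetaBinomial(60, a + x, b + 30 − x) ≥ 41). The cohort A prior is redacted. Assuming Beta(0.538, 1), with mean 0.538/1.538 = 35%, PPoS is 1.8% at 9/30 and 5.1% at 10/30. A cut at 9 fits a threshold near 5%, but cannot be strictly reproduced.

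**4. Exact effect of immaturity.** Let q be the share of eventual responses already confirmed at the interim. Then P(stop) = P(Bin(30, p·q) ≤ 9). Success also needs 41 of 90 at the end. If f is the share of participants with exactly two scans and s the share of responses first seen at scan 2, then q = 1 − f·s. For example, f = 0.5 and s = 0.2 give q = 0.90.

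| q | P(stop), ORR 50% | Success, ORR 50% | Type I error, ORR 35% |
|---|---|---|---|
| 1 | 2.1% | 82.2% | 2.4% |
| 0.95 | 4.0% | 81.3% | 2.4% |
| 0.90 | 6.9% | 79.5% | 2.3% |
| 0.80 | 17.6% | 72.1% | 1.9% |

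**5. Plausible q.** The documents give neither accrual nor response timing, so the following rests on assumptions: Poisson accrual, confirmation at the next 6-weekly scan, 15% discontinuing before week 12 without response, and cut-off when the first 30 enrolled are all evaluable (40,000 replicates). Results at true ORR 50%:

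| Accrual per month | Share first seen at scan 2 | P(stop) | Success |
|---|---|---|---|
| 3 | 20 / 30 / 40% | 3.4 / 4.2 / 4.9% | 81.6 / 81.3 / 80.8% |
| 5 | 20 / 30 / 40% | 4.3 / 5.8 / 7.5% | 80.8 / 80.6 / 79.3% |

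Against 82.2%, the loss is 82.2 − 81.6 = 0.6 to 82.2 − 79.3 = 2.9 points. If a further 10% of responses first appear at scan 3 (scan-2 share 20 to 30%), stops are 4.8 to 9.6% and success 80.7 to 77.6%, a loss of 1.5 to 4.6 points.

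**6. Milder settings.** At 1 to 2 a month with a scan-2 share of 10 to 40%, stops are 2.6 to 4.1%. With a cut-off 4 weeks later, at 3 to 5 a month and shares of 20 to 40%, they are 2.8 to 3.8%. Success is about 81 to 82% in both.

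**7. Waiting for pending responses.** If the confirmed count is 9 or fewer but confirmed plus pending reaches 10, recount at the last pending confirmatory scan. At 3 to 5 a month, P(stop) at ORR 50% returns to 1.9 to 2.2%, or 2.7 to 3.0% with 10% first seen at scan 3. At ORR 35%, P(stop) is 35 to 36% against 35.8% by plain binomial. It stays there when 2 or 5 percentage points of participants have a pending response that later fails confirmation.

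**The case against.** The governing document is unseen. How pending responses are scored is just the detail an interim plan would hold, and with the tables redacted nobody outside can tell whether the sponsor allowed for it. This stands, and the point is conditional for that reason.

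The effect is also small. Two scans are a minimum, so earlier enrollees may have three or more, and an unscheduled scan could confirm a response sooner. The population is narrow, so slow accrual is credible, and any gap before the cut-off lets responses mature. Many wrongly stopped cohorts sit near the boundary and would probably have failed anyway: under the prior assumed above, PPoS is about 5% at 10/30 and 12% at 11/30. All of this stands and sets the size given in the verdict.

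A reader might go further in three ways that the documents do not support.

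- **A serious loss of power.** The row with 80% confirmed (17.6% stops, 72.1% success), or accrual of 10 a month, would suggest one. Nothing in the documents supports either case.
- **A conflict over which 30 are analysed.** Protocol 4.1 and SAP 1.1 can be read as timing the interim, and SAP 2.15.1 as saying which data enter once it is triggered. These readings are compatible, and restricting the set to enrollment order would discard evaluable data.
- **An effect of the discontinuation wording.** SAP 1.1 and 2.15.1 refer to stopping study treatment. Protocol 4.1, 4.6 and 9.8.1 and SAP 2.15.2 refer to leaving the study. No effect on the responder count has been shown. It cannot be worked out cleanly either, because SAP 2.6.1 ("The BOR will be determined from response assessments undertaken while on treatment") and SAP 2.6.3 ("Tumor assessment data collected after discontinuation of study treatment for any reason will be included to derive BOR") disagree on which scans feed BOR.

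**Conclusion.** The point holds as a cheap improvement, provided the interim analysis plan does not already cover it. On the text available, the interim count can be too low but not too high. At true ORR 50% the false-stop chance rises from 2.1% to about 3 to 7% under accrual of 3 to 5 a month with 20 to 40% of responses first seen at scan 2. It is about 2 to 4% with slower accrual or a cut-off about 4 weeks later. Overall success falls by roughly 0 to 3 points, and by up to about 5 if some responses first appear at scan 3. These are assumption ranges, not estimates. A reader might infer a threat to type I error; there is none, since extra stopping can only lower it. Cohort B shares the two-scan structure, but with its boundary redacted no figure can be given.

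**What to change.** In SAP 2.15.1 and 2.15.2, protocol 9.8 and the interim analysis plan, state that the boundary applies to confirmed BIRC responses, and that futility is not declared while responses awaiting confirmation could lift the count above it. In that case, wait for the confirmatory scan and then apply the rule. Check that the PPoS and operating-characteristic tables match this definition. If the interim plan already says this, a cross-reference is enough.

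The cost is wording in three documents and a check of the tables. In operation, at 3 to 5 a month, the decision waits in about 1 to 6% of trials at ORR 50% and 5 to 17% at ORR 35%. The average wait is 4 to 5 weeks, and the longest about 6 weeks plus the scan window. At 5 a month, about 49 rather than 44 of the 90 are then enrolled at the decision. Correct stopping at ORR 35% stays at about 35 to 36%.

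Counting every unconfirmed response as a success is not asked for, nor is limiting the interim set to the first 30 enrolled. Using one discontinuation wording throughout is a clean-up only.
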